5. TREATMENT PLAN

5.1 Administration

• Capecitabine treatment will be administered on an **outpatient** basis with the exception that cycle 1 days 1 and 9 will be administered on the Clinical Research Unit for pharmacokinetic blood draws. No investigational or commercial agents or therapies other than those described below may be administered with the intent to treat the patient's malignancy.

- The minimum number of hours between capecitabine doses should be 10 hours.
- Subjects should then be instructed to take the capecitabine dose 30 minutes after eating a normal meal.

• Subjects will be provided with a Medication Diary for capecitabine, instructed in its use, and asked to bring the diary with them to each appointment. Subjects will be instructed on what to do if missed, skipped, or vomited dose, and how to record this information. Please see Appendix B for the medication diary template.

Capectabile Doslig								
	Cycle 1							
	Day 1	Days 2-7	Day 8	Day 9	Days 10-15	Day 16-		
	_	-	-	-	_	21		
Capecitabin e Dose*	(1,250mg/ m ² twice daily)	(1,250mg/ m ² twice daily)	none	(1,250mg/ m ² twice daily)	(1,250mg/ m ² twice daily)	none		
Weight	Ideal Body	Ideal Body	n/a	Actual	Actual	n/a		
Used for	Weight	Weight		Body	Body			
BSA				Weight	Weight			

Capeci	tabi	ine	Dosing
	-		-

* The final dose will be rounded to nearest 150mg due to available pill sizes.

Cycle 2 and beyond: Capecitabine 1,250mg/m² orally twice daily days 1-14 of a 21 day cycle, using actual body weight.

The Mosteller calculation and the patient's ideal or actual body weight will be used to calculate the BSA³ (calculations below).

Mosteller BSA formula: BSA (m²) = ([Height(cm) x Weight(kg)]/ 3600)^{1/2}

Ideal Body Weight (men) = 50 + 2.3 (Height in inches - 60) Ideal Body Weight (women) = 45.5 + 2.3 (Height in inches - 60)

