Hepatobiliary Hyperbilirubinemia Net chemred	22	9	2		

NA = Not Applicable

Clinical Pharmacokinetics

Capecitabine is relatively non-cytotoxic in vitro. This drug is enzymatically converted to 5-fluorouracil (5-FU) in vivo. Capecitabine is readily absorbed from the gastrointestinal tract. In the liver, a 60 kDa carboxylesterase hydrolyzes much of the compound to 5'-deoxy-5-fluorocytidine (5'-DFCR). Cytidine deaminase, an enzyme found in most tissues, including tumors, subsequently converts 5'-DFCR to 5'-deoxy-5-fluorouridine (5'-DFUR). The enzyme, thymidine phosphorylase (dThdPase), then hydrolyzes 5'-DFUR to the active drug 5-FU. Many tissues throughout the body express thymidine phosphorylase. Some human carcinomas express this enzyme in higher concentrations than surrounding normal tissues.³⁶ Following oral administration of capecitabine 7 days before surgery in patients with colorectal cancer, the median ratio of 5-FU concentration in colorectal tumors to adjacent tissues was 2.9 (range from 0.9 to 8.0).

The pharmacokinetics of capecitabine and its metabolites have been evaluated in about 200 cancer patients over a dosage range of 500 to 3500 mg/m²/day.^{14,37} Over this range, the pharmacokinetics of capecitabine and its metabolite, 5'-DFCR were dose proportional and did not change over time. The increases in the AUCs of 5'-DFUR and 5-FU, however, were greater than proportional to the increase in dose and the AUC of 5-FU was 34% higher on day 14 than on day 1. The elimination half-life of both parent capecitabine and 5-FU was about 3/4 of an hour. The inter-patient variability in the C_{max} and AUC of 5-FU was greater than 85%.

Capecitabine reached peak blood levels in about 1.5 hours (T_{max}) with peak 5-FU levels occurring slightly later, at 2 hours. Food reduced both the rate and extent of absorption of capecitabine with mean C_{max} and AUC_{0-infinity} decreased by 60% and 35%, respectively. The C_{max} and AUC_{0-infinity} of 5-FU were also reduced by food by 43% and 21%, respectively. Food delayed T_{max} of both parent and 5-FU by 1.5 hours. Plasma protein binding of capecitabine and its metabolites is less than 60% and is not concentration-dependent. Capecitabine was primarily bound to human albumin (approximately 35%).

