Capecitabine is extensively metabolized enzymatically to 5-FU. The enzyme dihydropyrimidine dehydrogenase hydrogenates 5-FU, the product of capecitabine metabolism, to the much less toxic 5-fluoro-5, 6-dihydro-fluorouracil (FUH₂). Dihydropyrimidinase cleaves the pyrimidine ring to yield 5-fluoro-ureido-propionic acid (FUPA). Finally, β-ureido-propionase cleaves FUPA to alpha-fluoro-β-alanine (FBAL) which is cleared in the urine.

Capecitabine and its metabolites are predominantly excreted in urine; 95.5% of administered capecitabine dose is recovered in urine. Fecal excretion is minimal (2.6%). The major metabolite excreted in urine is FBAL which represents 57% of the administered dose. About 3% of the administered dose is excreted in urine as unchanged drug.

Drug-Drug Interactions: (http://www.gene.com/gene/products/information/xeloda/pdf/pi.pdf)

Anticoagulants: In four patients with cancer, chronic administration of capecitabine (1250 mg/m² bid) with a single 20 mg dose of warfarin increased the mean AUC of S-warfarin by 57% and decreased its clearance by 37%. Baseline corrected AUC of INR in these 4 patients increased by 2.8 fold, and the maximum observed mean INR value was increased by 91%. Patients receiving concomitant capecitabine and oral coumarin-derived anticoagulant therapy should have their anticoagulant response (INR, PT) monitored closely with great frequency and the anticoagulant dose adjusted accordingly.

Drugs Metabolized by Cytochrome P450 Enzymes: In vitro enzymatic studies with human liver microsomes indicated that capecitabine and its metabolites (5'-DFUR, 5'-DFCR, 5-FU, and FBAL) had no inhibitory effects on substrates of cytochrome P450 for the major isoenzymes such as 1A2, 2A6, 3A4, 2C9, 2C19, 2D6, and 2E1.

Antacid/ Maalox[®] (20 mL), an aluminum hydroxide- and magnesium hydroxide-containing antacid, was administered immediately after capecitabine (1250 mg/m², n=12 cancer patients), AUC and C_{max} increased by 16% and 35%, respectively, for capecitabine and by 18% and 22%, respectively, for 5'-DFCR. No effect was observed on the other three major metabolites (5'-DFUR, 5-FU, FBAL) of capecitabine.

Capecitabine has a low potential for pharmacokinetic interactions related to plasma protein binding.

Based on the standard reference resources from the FDA

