(http://www.fda.gov/Drugs/DevelopmentApprovalProcess/DevelopmentResources/DrugInter actionsLabeling/ucm093664.htm) capecitabine is a weak inhibitor of CYP2C9. Thus, based on the drug interaction table in Appendix C, no medications would be contraindicated.

2.4 Hypothesis: Our hypothesis is that use of full weight based chemotherapy dosing will be associated with a significantly higher AUC and Cmax. The results of this study will advance oncologists' understanding of the potential impact of using limited weight-based dosing for capecitabine and provide preliminary data to demonstrate the need evaluate the importance of weight-based dosing for other chemotherapy and targeted agents.

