3.2 Exclusion Criteria

- 3.2.1 Patients who have had systemic chemotherapies or targeted therapies within 3 weeks or radiotherapy within 2 weeks prior to entering the study or those patients whose adverse events from prior therapies have not recovered to \leq grade 1 (other than grade 2 neuropathy, lymphopenia and alopecia which are permitted.)
- 3.2.2 Patients receiving any other investigational agents for cancer treatment.
- 3.2.3 Patients with treated, stable brain metastases are allowed to enroll. Patients must be at least 4 weeks from brain radiation and off any medications used to treat brain metastases including steroids. Patients are allowed to be on anti-epileptic medications that are not contraindicated as listed in Appendix C.
- 3.2.4 Patients with any condition of the gastrointestinal tract that is expected to result in an inability to swallow or absorb oral medications (ie. prior surgical procedures affecting absorption and requiring i.v. alimentation). This will be determined at the discretion of the PI.
- 3.2.5 Patients may not be taking any concomitant drugs that are contraindicated based on the drug-interaction table in Appendix C.
- 3.2.6 Concurrent treatment with warfarin (coumadin) is allowed, but close monitoring of the PT/INR is recommended.
- 3.2.7 Uncontrolled intercurrent illness including, but not limited to, ongoing or active severe infection, symptomatic congestive heart failure, unstable angina pectoris, clinically significant or symptomatic cardiac arrhythmia, other malignancies requiring therapy or psychiatric illness/social situations that would limit compliance with study requirements.

- 3.2.8 Pregnant women or women who are breastfeeding are excluded from this study because capecitabine is a pregnancy category D drug and is known to pass to the infant in breastmilk.
- 3.2.9 Patients with known deficiency of the dihydropyrimidine dehydrogenase (DPD) enzyme.
- 3.2.10 History of allergic reactions attributed to compounds of similar chemical or biologic composition to capecitabine.

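### Nothing in the plan restricts or records antacid use at the two PK doses, although Section 2.3 reports that an antacid taken right after capecitabine raised parent Cmax by 35% and AUC by 16%

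*Combined protocol and SAP*

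**What the plan says.** Section 13.1 makes capecitabine AUC and Cmax the primary endpoints and compares ideal-weight with actual-weight dosing by a paired t-test. The two full profiles come from C1D1 and C1D9: "cycle 1 days 1 and 9 will be administered on the Clinical Research Unit for pharmacokinetic blood draws" (5.1), with samples to 8 hours (9.1, 9.2).

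The drug-interaction text in Section 2.3 describes 20 mL of an aluminium/magnesium hydroxide antacid in 12 patients at 1250 mg/m². It "was administered immediately after capecitabine", and parent AUC and Cmax "increased by 16% and 35%, respectively, for capecitabine". For 5'-DFUR, 5-FU and FBAL: "No effect was observed on the other three major metabolites". Whether those patients had eaten is not stated.

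The restriction on other drugs is 3.2.5: "Patients may not be taking any concomitant drugs that are contraindicated based on the drug-interaction table in Appendix C". Section 2.3 classes capecitabine as a weak CYP2C9 inhibitor and concludes from the same table that "no medications would be contraindicated".

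Section 5.1 sets a 10-hour minimum dose interval and tells patients to "take the capecitabine dose 30 minutes after eating a normal meal". Section 5.2 deals with warfarin, bone agents, antiemetics, colony-stimulating factors and antidiarrhoeals. Section 9 gives sampling times without medication conditions. In the Section 10 calendar, Concurrent Meds is marked at Pre-Study, Day 1 of cycle 2 onward and Off Study, with no mark in cycle 1.

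**The concern.** The protocol reports that a common over-the-counter product changes the primary-endpoint analyte at the trial's own mg/m² dose, then sets no condition for it. The screen it relies on cannot catch the problem, because it addresses enzyme interactions and ends with nothing contraindicated.

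Pairing protects against stable differences between patients. It does not protect against a condition that differs between the two days. An antacid taken right after the dose on Day 9 only would push that patient's difference up; on Day 1 only, down. With 10 patients, one discordant pair is 10% of the data. Without a record on the day, nobody could later say reliably whether an outlying pair reflected dose or an antacid.

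**Working it through.** **1. Inputs.** Section 13.2: difference 30%, SD 25% (Table 13.1 also shows 20% and 30%), n = 10, significance level 0.025 per endpoint. Section 2.3: antacid effect +35% on Cmax, +16% on AUC. Assumed, because the documents give no rate of use: one of the 10 patients takes the antacid on one PK day only and shows the full effect. Differences are in percent of the antacid-free Day 1 value, normally distributed.

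**2. The plan's own figures.** Paired-t power uses a noncentral t with 9 degrees of freedom and noncentrality (difference/SD) × √n.
- 30/25 × √10 = 3.79 against a two-sided 0.025 critical value of 2.685: power 84.2% (plan: 82%).
- 25/25 × √10 = 3.16: power 68.2% (plan: 68%).
- All 15 cells of Table 13.1 reproduce at two-sided 0.025, including n = 10.
- The text of 13.2 also says one-sided 0.025, which would give 92.0% and 80.3%. The stated figures fit the two-sided level, so that is used below.
- At SD 20%: 30/20 × √10 = 4.74, power 96.4%.

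**3. One Day-1-only user.** Two ways to apply the effect:
- Difference scale: subtract 35 or 16 points from that pair. The mean shifts by −35/10 = −3.5 (Cmax) or −16/10 = −1.6 (AUC).
- Ratio scale: divide that pair's Day 9/Day 1 ratio by 1.35 or 1.16. For Cmax, 1.30/1.35 = 0.963, so the pair moves from +30 to −3.7 and the mean by −3.4. For AUC, 1.30/1.16 = 1.121, so the mean moves by −1.8.

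Power by simulation (400,000 trials), two-sided 0.025; ranges run across the two scales:

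| | No antacid | Cmax | AUC |
|---|---|---|---|
| SD 25% | 84% | 66–70% | 78–79% |
| SD 20% | 96% | 84–88% | 93–94% |
| SD 25%, half the effect | 84% | 78% | 82% |

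At one-sided 0.025 and SD 25%, full effect, power falls from 92% to 80–83% for Cmax and 88–89% for AUC.

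**4. One Day-9-only user.** Multiply the Day 9 value by 1.35 or 1.16. The mean shifts by 1.30 × 35/10 = +4.55 points (Cmax) or 1.30 × 16/10 = +2.08 points (AUC). Power at SD 25% is 85–86%. The cost is an inflated estimate, to be set against a standard error of 25/√10 = 7.9 points.

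**5. Dropping the discordant pair.** With n = 9 and SD 25%, power is 78.1%, no better than keeping the pair for AUC (78–79%). Exclusion does not recover the planned power.

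**The case against.** The strongest reply is that the triggering event is narrow. The effect was shown for one antacid taken right after the dose. Here it would have to be taken then, on one PK day only, by a patient dosed on the Clinical Research Unit. The plan does not recommend antacids, and gives no rate of use. Trial doses follow a meal, and Section 2.3 says "Food reduced both the rate and extent of absorption of capecitabine", so the +35% may not carry over. All of this stands, and it is why no probability or expected loss is attached to the point.

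Partial safeguards exist. Appendix C has nurses take medications with route and schedule from study candidates and has over-the-counter drugs reviewed, so regular users should be known at entry. Equal use on both days cancels on a log scale, and 13.1 allows a transformation if data are non-normal. On untransformed differences a small residue remains: 30 × 0.35/10 = 1.05 points for Cmax. The diary has a comments column. These lower the risk, but none requires antacid use to be avoided or noted at the PK doses.

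An unmarked calendar cell is also weak evidence that nothing would be recorded. The adverse-event row is marked only at Pre-Study and Off Study, yet 6.1 requires toxicity to be judged on Day 1 of each cycle. The supportable statement is that no record is scheduled, not that none would be made.

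A reader might infer that the trial should expect power near 66%. The documents do not support that. The figure needs Day-1-only use, the full effect, the difference scale and an SD of 25%, which 13.2 presents as an upper bound and calls overall, so it may already absorb incidental co-medication. Day 1 also precedes any study-drug effect; Table 2 lists dyspepsia in 8% of patients on capecitabine, so drug-related use is more plausible on Day 9, where power is essentially unchanged.

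**Conclusion.** The gap is real and minor: an interaction that the protocol itself reports for the primary-endpoint analyte is neither controlled nor scheduled for recording at the two doses that carry the primary comparison. It is a low-probability risk to precision and interpretation.

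The sizes above are scenarios for one patient in 10 at the full Section 2.3 effect, not expected losses. At SD 20%, power stays above 80% for both endpoints even with a Day-1-only user.

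Two stronger readings should be resisted. One is that the comparison is biased because +35% exceeds the 30% minimal important difference. The +35% applies to an exposed dose; one user in 10 moves the Cmax mean by 3.4 to 4.6 points, and the documents give neither frequency nor direction of use. The other is that active-drug exposure is affected: Section 2.3 reports no effect on 5-FU, so the point concerns the parent-drug endpoints only.

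**What to change.** - **Section 5.1:** ask patients not to take aluminium/magnesium antacids around the C1D1 and C1D9 PK doses, from shortly before the dose until about 4 hours after it, unless medically needed. Section 2.3 puts parent Tmax at about 1.5 hours and the food delay at 1.5 hours, so 1.5 + 1.5 = 3 hours and a 4-hour window covers the expected peak. Extending it to the 8-hour sample would go beyond an effect shown only for an antacid taken immediately after dosing.
- **Section 10:** mark Concurrent Meds on C1D1 and C1D9, including over-the-counter antacids with time taken. This matters most, since it cannot be reliably rebuilt later.
- **Section 13.1:** report any pair with antacid use on one PK day only descriptively, without excluding it from the primary test.

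The cost is a minor restriction on two days and two short entries at visits already held on the Clinical Research Unit. The sample size and primary test do not change.

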13.2 Sample Size/Accrual Rate

The primary objective is to characterize the effect on pharmacokinetic parameters when capecitabine is dosed on actual versus ideal body weight results in obese patients with advanced solid tumors. A mean difference in the AUC and Cmax of at least 30% between the ideal body weight dosing versus the actual body with based dosing will be considered as a minimal important difference. Based on the results of several previous PK studies involving capecitabine, it is anticipated that the overall standard deviation for the difference between the two dosing strategies is at most 25% of the mean difference. The following table shows the required sample sizes to detect various mean differences in PK parameters between the two dosing strategies at the two-sided 0.025 (=0.05/2 - a Bonferroni adjustment for comparing both AUC and Cmax) significance level with 80%

power, assuming a standard deviation ranging from 20-30%.

with 0070	power ai me inc	biaca 0.025 sig	infleance level				
	Mean difference in PK parameters between the ideal versus actual weight based dosing strategy						
Standard	20%	25%	30%	35%	40%		
Deviation							
20%	13	9	7	6	6		
25%	18	13	10	8	7		
30%	24	17	13	10	9		

Table 13.1: *Required sample sizes to detect various mean differences in PK parameters with 80% power at the two-sided 0.025 significance level*

A sample size of n=10 patients is proposed for this study. With a sample size of 10 patients, a clinically important difference of 30% between the ideal and actual body weight based dosing will be detected with 82% power at the one-sided 0.025 (=0.05/2 - a Bonferroni adjustment for evaluating both AUC and Cmax) significance level, assuming an overall standard deviation of 25%. A mean difference of only 25% will be detected with 68% power. Patients will be evaluable for the primary endpoint if he or she completes cycle 1, capecitabine therapy without dose reduction or skipped doses. Any patient who does not meet these criteria will be replaced.

The anticipated accrual is 1-2 patients per month. Therefore, the study is expected to be completed within 6-12 months after first accrual.

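### The meal before the two pharmacokinetic doses (cycle 1 Days 1 and 9) is neither matched nor recorded, although the protocol reports a large food effect; the exposure is mainly in Cmax

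*Combined protocol and SAP*

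**What the plan says.** Section 5.1 states that "cycle 1 days 1 and 9 will be administered on the Clinical Research Unit for pharmacokinetic blood draws". Its only meal rule is general: subjects are to "take the capecitabine dose 30 minutes after eating a normal meal". The pill diary in Appendix B also asks for dosing 30 minutes after eating, at about the same time each day, without describing the meal.

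I found no further meal condition in the places where one would be expected: the evaluability rules (Sections 5.6 and 11.1.1), the sampling plan (Sections 9.1 and 9.2), the study calendar (Section 10) or the analysis (Section 13.1). Evaluability turns on the share of doses taken.

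Section 2.3 (Clinical Pharmacokinetics) says "Food reduced both the rate and extent of absorption of capecitabine", with mean Cmax and AUC "decreased by 60% and 35%, respectively". For 5-FU the two parameters "were also reduced by food by 43% and 21%, respectively". Food also delayed Tmax by 1.5 hours. Section 13.1 makes capecitabine AUC and Cmax the primary endpoints, compared by paired t-test. Section 13.2 plans for a 30% difference in 10 patients, "assuming an overall standard deviation of 25"%.

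**The concern.** The primary analysis uses one within-patient difference per endpoint: Day 9 minus Day 1. Whatever else differs between those two mornings enters that difference. The protocol itself names food as a strong influence on both endpoints, leaves the meal to habit on the two days that matter, and keeps no record that would let anyone check afterwards.

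Two consequences need to be kept apart. Meal differences that vary at random from patient to patient widen the SD of the paired difference and cost power. A difference running the same way in most patients shifts the mean, and the fixed order cannot cancel it, because Day 1 is always ideal weight and Day 9 always actual weight. Lighter eating on Day 9, for instance, would tend to raise exposure and look like the effect in the study hypothesis. That direction is only an illustration; the documents hold no data on what patients eat on either day.

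**Working it through.** **Inputs.** From Section 13.2: n = 10, difference 30%, SD 25%, alpha 0.025 per endpoint. From Section 2.3: fed/fasted ratio 1 − 0.60 = 0.40 for Cmax and 1 − 0.35 = 0.65 for AUC. From Section 5.1: the Mosteller and ideal-weight formulas. From Section 3.1.3: BMI of at least 30.

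**Step 1: the plan's own figures.** I used paired t power from the noncentral t distribution, with noncentrality (difference/SD) × √n = (30/25) × √10 = 3.79 on 9 degrees of freedom.
- Two-sided 0.025 gives 84.2% for a 30% difference (stated: 82%) and 68.2% for a 25% difference (stated: 68%). All 15 cells of Table 13.1 reproduce on this basis.
- One-sided 0.025 would give 92.0% and 80.3%. The text calls the n=10 power one-sided, but only the two-sided reading fits its figures. I use two-sided, so the reference power is 84%.

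**Step 2: the dose contrast being measured.** Section 2.3 says the pharmacokinetics of capecitabine and its metabolite 5'-DFCR "were dose proportional and did not change over time", so the expected exposure ratio is about the dose ratio. Height cancels in the Mosteller formula, leaving √(actual weight / ideal weight).
- Woman, 60 in, BMI 30: actual 30 × 1.524² = 69.7 kg, ideal 45.5 kg, ratio √(69.7/45.5) = 1.24.
- Man, 72 in, BMI 30: actual 30 × 1.8288² = 100.3 kg, ideal 50 + 2.3 × 12 = 77.6 kg, ratio √(100.3/77.6) = 1.14.

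Over heights 60-72 in and both sexes, before rounding to 150 mg:

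| BMI | Actual/ideal dose ratio |
|---|---|
| 30 | 1.14-1.24 |
| 35 | 1.23-1.34 |
| 40 | 1.31-1.43 |

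**Step 3: the ceiling set by food.** The fasted/fed ratio is 1/0.40 = 2.50 for Cmax (log range 0.916) and 1/0.65 = 1.54 for AUC (log range 0.431). The share of that range by which two meals must differ to equal a given dose ratio is ln(ratio)/log range:

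| Dose ratio | Cmax | AUC |
|---|---|---|
| 1.2 | 0.182/0.916 = 20% | 0.182/0.431 = 42% |
| 1.3 | 0.262/0.916 = 29% | 0.262/0.431 = 61% |

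**Step 4: random meal differences.** Assumption: each day's meal effect is independent and uniform over a share f of the log range, and is additional to the 25% SD. A uniform variable of width w has variance w²/12, so the difference of two has SD f × (log range)/√6. Log units are read as percentages, which is an approximation. Total SD = √(25² + meal SD²).

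| Endpoint | f | Meal SD | Total SD | Power, 30%, n=10 | n for 80% |
|---|---|---|---|---|---|
| Cmax | 0.25 | 9.4% | 26.7% | 79% | 11 |
| Cmax | 0.50 | 18.7% | 31.2% | 64% | 13 |
| AUC | 0.25 | 4.4% | 25.4% | 83% | 10 |
| AUC | 0.50 | 8.8% | 26.5% | 79% | 11 |

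**Step 5: a systematic difference.** If Day 9 meals were lighter in every patient by a share s of the log range, the observed ratio would be multiplied by (fasted/fed)^s. At s = 0.10 that is 2.50^0.10 = 1.10 for Cmax and 1.54^0.10 = 1.04 for AUC. At s = 0.25 it is 1.26 and 1.11. Heavier Day 9 meals would give the reciprocals. These values of s are illustrative.

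**The case against.** The strongest reply is that the 60% and 35% figures answer another question. They compare food with no food, whereas both profiled doses follow a meal by the same 30 minutes. This stands: a reader might infer that the food effect outweighs the dosing effect under test, but the documents do not support that. The figures bound the problem and do not estimate it. For AUC, two fed doses would have to differ by 42-61% of the whole fed-fasted range to equal a dose ratio of 1.2-1.3.

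Second, the 25% SD is said to rest on previous capecitabine studies and may already contain ordinary meal variation. This also stands. The documents do not say, so the power losses in Step 4 may count some variation twice.

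Third, a shift in one patient is not a shift in the mean of ten. Random differences partly average out, and nothing in the documents shows a systematic one. This is right, and it is why bias remains only a possibility.

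Fourth, one might call food the largest documented influence on the endpoints, or say that meal timing is left open. Neither holds. Exposure to capecitabine is reported as dose proportional over 500 to 3500 mg/m²/day, a sevenfold range, so dose is the larger influence. The meal-to-dose interval is already fixed at 30 minutes.

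None of these replies supplies a rule that makes the two meals alike, or a record of them.

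**Conclusion.** The point holds as a low-cost improvement to the design. The plan as written leaves an avoidable, unobserved source of variation in both primary endpoints of a 10-patient paired study. Its true size cannot be derived from the documents. Under the assumption in Step 4, power drops from 84% to between 79% and 64% for Cmax, and only to between 83% and 79% for AUC, so the concern is chiefly about Cmax.

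Bias is a further possibility because of the fixed order. It would matter most at the eligibility floor of BMI 30, where the dose contrast is 14-24%, and less at BMI 35 (23-34%) or BMI 40 (31-43%). The documents do not show that meals will differ systematically, nor that meal differences will match the dosing effect.

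**What to change.** Add one sentence to Section 5.1, with a matching line in Section 9.2, for cycle 1 Days 1 and 9 only: the Clinical Research Unit serves the same meal on both days at the same clock time, dosing follows at the existing 30-minute interval, and the amount eaten is recorded. The record would permit a sensitivity check for patients whose intake differed between the days. The instruction for home doses stays as it is, and sample size, doses and sampling times are untouched.

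The cost is a meal order on a unit where the patient already is, a short record, and slightly less everyday eating conditions on two days.
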